The preclinical studies at BU testing the BP in a diabetic swine model of T1D (3-4), and all of the inpatient clinical trials in the Clinical Research Center at MGH testing the BP in adults and adolescents with T1D (5-7) set the stage for the outpatient studies that followed. In November 2012 we obtained FDA approval to conduct our first outpatient study testing our BP in adults 21 years or older with T1D. This study, which we referred to as the Beacon Hill Study, followed a random-order cross-over design in which 20 adults with T1D participated in 5 days on our iPhone-based BP and 5 days of usual care in which they wore a CGM with blinded display and muted alarms. In the BP arm, subjects kept to a three-square-mile geographic area centered around the Beacon Hill neighborhood in Boston. They ate as they chose at local restaurants, and exercised at will with access to two gyms. Analysis was pre-specified to focus on Days 2--5, since glycemic control is more representative of BP performance after most of the adaptation by the BP occurs on Day 1 (8). Results are summarized in the plots and table of Figure 1.

| Study | Age (years) | Bionic Pancreas (BP) | | | Control | | | p-value (BP versus Control) for: | | |
|--|-------------|--------------------------------|--|------------------|--------------------------------|--|------------------|----------------------------------|------------------------------------|--------------------------------------|
| | | Mean CGM glucose level (mg/dl) | % of CGM glucose levels < 60 mg/dl (%) | 70–180 mg/dl (%) | Mean CGM glucose level (mg/dl) | % of CGM glucose values < 60 mg/dl (%) | 70–180 mg/dl (%) | Mean CGM glucose level | % of CGM glucose values < 60 mg/dl | % of CGM glucose values 70–180 mg/dl |
| Beacon Hill (n=20, 5-day experiments) | ≥21 | 133 | 1.5 | 80 | 159 | 3.7 | 59 | <0.001 | 0.020 | <0.001 |
| 2013 Summer Camp (n=32, 5-day experiments) | 12–20 | 142 | 1.3 | 76 | 158 | 2.2 | 65 | 0.004 | 0.192 | <0.001 |
| 2014 Summer Camp (n=19, 5-day experiments) | 6–11 | 137 | 1.2 | 81 | 168 | 2.8 | 58 | 0.004 | 0.001 | <0.001 |
| BP Multi-Center (n=39, 11-day experiments) | ≥18 | 141 | 0.6 | 78 | 162 | 1.9 | 62 | <0.001 | <0.001 | <0.001 |

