We hypothesize that the iLet BP will be non-inferior to the iPhone-based BP in dose administration and blood glucose control while subsequently improving user satisfaction with the device. We also hypothesize that Xeris glucagon in the iLet BP will be non-inferior to Lilly glucagon in the iLet BP in both infusion site reactions and occlusions.

In the Infusion Set Sub-Study, we hypothesize that the iLet infusion set will be non-inferior to the Contact Detach infusion set in plasma insulin levels, blood glucose control, and user experience.

The specific aims of this study are:

Aim 1. To conduct an outpatient study testing the safety and efficacy of the iLet BP versus our iPhone-based BP in up to 10 adult (≥ 18 years of age) subjects with type 1 diabetes in the fasted state, after a meal, and during and after exercise.

The study for this Aim will consist of two 8-hour study arms in random order: one with the iPhone-based BP and one with the iLet BP. Subjects will arrive fasting and remain fasted until the lunch meal. They will exercise on a stationary bike bpm for approximately 30 minutes with a heart rate from 120–140, starting at least 2 hours after lunch. The primary outcome will be the average percent dose amounts of both insulin and glucagon calculated by the control algorithm that are successfully delivered by the pump. Important secondary outcomes will include other metrics of device function (plasma insulin and glucagon levels will be measured every 30 minutes throughout the experiment) and measures of glycemic regulation, including mean CGM glucose and hypoglycemia exposure (% time <60 mg/dl).

Aim 2. To conduct an outpatient study testing the safety and efficacy of the iLet BP with Lilly glucagon versus Xeris glucagon in up to 10 adult (≥ 18 years of age) subjects with type 1 diabetes

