The primary analysis of the designated endpoints will be calculated on an intention-to-treat basis. In cases where an arm was not completed (and that arm was not repeated according to protocol criteria) we will use the available data from that arm in the data analysis. We will only include arms that were started by the subject.

We will use the Shapiro-Wilk test to determine the normality of the residuals for each comparison and calculate percentages, means or medians, and standard deviation and/or ranges as appropriate in descriptive analyses. We will use paired t-test or the Wilcoxon signed rank test for comparison of means with normally or non-normally distributed residuals, respectively. In a secondary analysis we will look for any period effect and any interaction between treatment and period, although no such interaction is predicted for the primary outcome, and there is probably insufficient power to identify a small interaction.

VI. c. Power Analysis

The power analysis is based on data from previous studies using the iPhone-based BP. The following table shows the percentage of time that the insulin and glucagon pumps were available to deliver doses calculated by the bionic pancreas. When pumps were not available, this was typically due to loss of communication between the iPhone and the t:slim pumps, but could also be due to pump occlusion or inadequate drug in the reservoir, among many other possible reasons.

Table 1. Time that pumps were available in previous bionic pancreas studies

| Study | insulin | | Glucagon | |
|------------------------------|---------|-----|----------|-----|
| | Mean | SD | Mean | SD |
| Beacon Hill | 96.5 | 2.7 | 95.9 | 2.3 |
| Camp1 | 93 | 2.7 | 92.2 | 2.3 |
| Camp2 | 95.1 | 2.5 | 93.9 | 3.1 |
| Multi-center | 96.1 | 2.5 | 95.9 | 2.5 |
| Mean | 95.2 | 2.6 | 94.5 | 2.6 |
| Min | 93.0 | 2.5 | 92.2 | 2.3 |
| Max | 96.5 | 2.7 | 95.9 | 3.1 |
| ttest (insulin vs. glucagon) | | | 0.044 | |

The glucagon pump was unavailable a greater percentage of the time than the insulin pump in the iPhone-based BP. This could be due to more frequent reservoir changes (the glucagon reservoir had to be changed every day, while the insulin reservoir was changed every other day – the pumps were unavailable during the reservoir change process), greater number of occlusions in the glucagon tubing and infusion sets, or possibly other, unknown factors.

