We anticipate that the iLet BP will be much more reliable in terms of delivering calculated doses because it does not rely on wireless communication between the device running the control algorithm and the pumps. In the iLet, the control algorithm and pumps are integrated into a single device. Nonetheless, there may still be times that the pump is unavailable or that the full dose is not delivered (e.g. due to temporary loss of communication between components due to software issue, tubing occlusion, or inadequate drug in the reservoir). Therefore, we anticipate that the percentage of the dose amount calculated that are delivered will be substantially greater, but not 100%.

We have modeled the power to detect a difference between the iPhone-based and iLet BPs based on an aggregate rate of pump unavailability of the iPhone-based BP (including both the insulin and glucagon pumps) of $96\pm 2.5\%$, which is close to the maximum reliability that we observed in the more reliable insulin pump across the 4 previous studies. We then calculated the power based on different possible reliabilities of the iLet internal pumping systems, based on 2-fold, 5-fold, and 10-fold reductions in pump unavailability, corresponding to availabilities of $98\pm 2.5\%$, $99.2\pm 2.5\%$, and $99.6\pm 2.5\%$, respectively. Under these assumptions, the sample sizes required for each of these possible outcomes to achieve a power of 80% with an alpha of 5% using a 2-sided test are 25 subjects, 10 subjects, and 8 subjects respectively. We expect a reduction of at least 5-fold in pump unavailability (and 10-fold would not be surprising), so 10 subjects should provide sufficient power to detect a difference. The standard deviations are assumed to be unchanged in these calculations, although it is likely that the standard deviations would also be reduced if the pump becomes more reliable - this means that the sample size estimates are likely conservative.

As the Infusion Set Sub-Study is a pilot study of the modified infusion set, no formal power calculations have been done for this portion of the study.

VI. d. Criteria for Success of the Study

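### The 25/10/8 sample sizes come from a normal approximation; the planned paired t-test has 72% power, not 80%, at 10 subjects on the plan's inputs, and no 8-hour SD supports calling them conservative

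*Combined protocol and SAP*

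**What the plan says.** Section VI.c models the iPhone-based system at 96±2.5% pump availability. It calls this level "close to the maximum reliability that we observed in the more reliable insulin pump across the 4 previous studies". The iLet is set at 98, 99.2 or 99.6%, each ±2.5%, for 2-, 5- and 10-fold reductions in unavailability. The sample sizes "to achieve a power of 80% with an alpha of 5% using a 2-sided test are 25 subjects, 10 subjects, and 8 subjects respectively". The section expects at least a 5-fold reduction, "so 10 subjects should provide sufficient power to detect a difference". It adds that the iLet SD would probably be smaller than assumed, and "this means that the sample size estimates are likely conservative".

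The analysis text at the end of section VI.b reads: "We will use paired t-test or the Wilcoxon signed rank test for comparison of means", the choice depending on whether the residuals are normal.

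The means and SDs come from Table 1 in VI.c: "The following table shows the percentage of time that the insulin and glucagon pumps were available to deliver doses". The experiments behind it lasted 5 or 11 days per subject; the longest is listed in section I.c as "BP Multi-Center (n=39, 11-day experiments)". For this trial, Aim 1 in section II states: "The study for this Aim will consist of two 8-hour study arms in random order". The Aim 1 primary endpoint in VI.b.1 is the average percent of calculated dose amounts that the pump delivers, insulin and glucagon combined.

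**The concern.** A paired t-test on 10 subjects has 9 degrees of freedom. At that size a normal approximation understates the number needed, so power at n = 10 may fall below the quoted 80%. The quantity that a paired analysis needs, the SD of the within-subject difference, is not stated.

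A second doubt is whether the SD of 2.5 applies here. It belongs to a different measure (time available) averaged over a much longer window (days). The argument for conservatism weighs only a possibly smaller iLet SD.

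This matters because VI.d makes a significant improvement in this outcome a main criterion for success, and IV.a plans for at most 10 completers, leaving no spare subjects. If the study ends without significance, readers will judge that result against a 20% chance of missing a true 5-fold gain. The plan's own inputs give a higher chance.

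**Working it through.** **Inputs (section VI.c).** Two-sided alpha 0.05, target power 80%, SD 2.5 in each arm, iPhone-based availability 96% (the sentence labels it unavailability, but the figure is an availability). The differences are:
- 2-fold: 98 − 96 = 2.0 points
- 5-fold: 99.2 − 96 = 3.2 points
- 10-fold: 99.6 − 96 = 3.6 points

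**Step 1: reproduce the plan.** Normal formula, n = (1.960 + 0.842)² × 2 × 2.5² / d²:
- d = 2.0: 24.53, rounds up to 25
- d = 3.2: 9.58, rounds up to 10
- d = 3.6: 7.57, rounds up to 8

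This matches 25/10/8 exactly. Read as a paired calculation, it implies an SD of the difference of 2.5 × √2 = 3.54, that is, zero within-subject correlation. Taking 2.5 itself as the SD of the difference does not match: the normal formula then gives 13/5/4 and the paired t-test 15/7/6. A scan of the SD of the difference from 2.3 to 4.0 found no value at which a paired t-test gives 25, 10 and 8 together.

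**Step 2: the planned test on the same inputs.** Paired t-test, non-central t with n − 1 degrees of freedom and non-centrality d√n / 3.54:

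| Reduction | d | Plan's n | Power at plan's n | n for 80% | Power at n = 10 |
|---|---|---|---|---|---|
| 2-fold | 2.0 | 25 | 77% | 27 | 36% |
| 5-fold | 3.2 | 10 | 72% | 12 | 72% |
| 10-fold | 3.6 | 8 | 70% | 10 | 82% |

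A simulation of 400,000 trials at n = 10, d = 3.2 gave 72.3%. For 5-fold, 9 completers give 66% and 8 give 60%.

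**Step 3: what would restore 80% at n = 10 for 5-fold.** The SD of the difference must be 3.21 or less. Changing one input at a time:
- Correlation of about 0.17 with both SDs at 2.5. Correlations of 0, 0.1, 0.2 and 0.3 give 72, 77, 81 and 86%.
- iLet SD of about 2.0 at zero correlation. SDs of 2.5, 2.0 and 1.5 give 72, 80 and 87%.
- iPhone-based availability of 95.6% or lower, since 0.8 × (100 − 95.6) = 3.52. Baselines of 96, 95.5 and 94.85% give 72, 82 and 91%. The last is the average of the two Table 1 means, (95.2 + 94.5)/2.
- From 96%, a reduction of about 8.4-fold or more: 4 × (1 − 1/8.4) = 3.52.

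The correlations and reduced iLet SDs are assumptions; the documents give neither.

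**Step 4: the source of the SD.** Table 1 reports percent of time available over 5 or 11 days. The trial measures percent of dose amount over 8 hours. An average over 8 hours is probably noisier than one over days, but nothing in the documents lets one compute by how much. The tolerance can be computed. At the favourable 94.85% baseline the 5-fold difference is 0.8 × 5.15 = 4.12, and 80% at n = 10 holds only while the SD of the difference stays at or below 4.14. That is 17% above the implied 3.54 (4.14/3.54 = 1.17).

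**The case against.** **Distribution.** A percentage near 99 with an SD of 2.5 is pressed against its ceiling and cannot be normal, so 72% is less exact than it looks. Simulation from beta distributions with the plan's means and SDs, at zero correlation, gives the paired t-test about 79% at n = 10. This stands as a caveat. But the plan's own formula uses the normal model, and the beta shape is itself an assumption. With normal differences, the Wilcoxon fallback gives about 70%.

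**Conservatism has a stated reason.** A more reliable pump may well be less variable. If the iLet SD fell 5-fold to 0.5, power at n = 10 would be 94%. That is plausible, but the plan does not quantify it or weigh it against the shorter window.

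**Five-fold is the plan's floor.** True: 10-fold gives 82%. But the choice of 10 subjects is argued from 5-fold.

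**The visits differ from the earlier studies in both directions.** Table 1 may include downtime from reservoir changes, and here an RN or MD is present throughout. The net effect on the mean and SD is therefore unknown, which is a reason to re-estimate both rather than to assume either direction.

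**Availability is a declared proxy.** VI.b.3 explains that a calculated dose is not issued unless the pump can be reached, so time and dose are linked. That makes the mean a reasonable starting point, but supplies no SD for the dose endpoint.

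**Completers and baseline.** Enrolment of up to 20, repeat visits and use of partial data make fewer than 10 analysed subjects less likely. The 94.85% baseline includes the two youth camps; the two adult studies average (96.5 + 95.9 + 96.1 + 95.9)/4 = 96.1%, close to the plan's 96%. Both points are fair. Neither changes the 72%, which uses n = 10 and 96%.

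**Conclusion.** The concern holds. As written, the calculation does not show 80% power at 10 subjects for the test the plan will use. On its own inputs the figure is 72% for a 5-fold reduction, so a true gain of that size would be missed in about 28% of trials instead of 20%. This rests on normally distributed differences, an SD of 2.5 in each arm and zero correlation, all of which the plan's own 25/10/8 implies. The shift in sample size is only two subjects per scenario, and modest, plausible changes in one input would bring power back to 80%. The defect is therefore an unsupported power statement, not proof that the study is too small.

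The conservatism claim is also unsupported: no SD is given for an 8-hour window, for the dose-amount endpoint or for the paired difference.

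**What to change.** In section VI.c:

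1. Name the paired t-test as the basis for power, and state that 10 subjects give 36%, 72% and 82% for 2-, 5- and 10-fold reductions, with 12 needed for 80% at 5-fold.
2. State the assumed SD of the paired difference (3.54 on present inputs), and show the range over correlation, iLet SD and baseline. Note that the figures assume normal differences although the measure is capped at 100%.
3. Where the earlier records allow, recompute the mean and SD from 8-hour windows on the dose-amount endpoint, and quote the resulting power.
4. Delete the statement that the estimates are conservative unless step 3 supports it.

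The cost is one corrected paragraph and a modest re-analysis of existing data. The stated power will look less favourable. No change to enrolment, endpoint or analysis method is asked for.

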Our current bionic pancreas system utilizes an iPhone running the control algorithm and Dexcom G4 CGM combined in a customized control unit, which then communicates via Bluetooth to two tandem t:slim insulin pumps. Naturally, connection is lost between these four devices at multiple times throughout the day, which has the potential to impact blood glucose control due to missing CGM values or missed doses. In addition, the troubleshooting required to repair these connections can be a burden on the wearer. Integrating these parts into one combined device would eliminate the need to maintain constant connections, optimizing blood glucose control, ease of use and quality of life.

We have designed, built, and tested our first-generation working prototype BP system, which we refer to as the iLet, and which consists of a dual-chamber autonomous infusion pump integrated with a CGM receiver and printed circuits that run the control algorithm. The current study is designed to test the iLet BP in human subjects for the first time in comparison with our iPhone-based system to establish equivalence between the two systems (primarily in terms of functionality, user safety, accuracy, and component reliability), and allow us to move forward with larger studies using the iLet BP (where comprehensive efficacy through continuous full daily use will be established).

The iLet BP is capable of using a new formulation of glucagon that is non-aqueous and is much more stable. This formulation, produced by Xeris pharmaceuticals, is stable for at least 2 years at room temperature. However, this formulation is not compatible with plastics used in the Tandem t:slim pump and standard infusion sets. The iLet BP and its new infusion set have been designed to be fully compatible with the Xeris glucagon formulation.

A custom infusion set is required for this bihormonal system, to prevent future consumers from being able to accidentally swap their insulin and glucagon reservoirs and infusion sets, which could be potentially fatal. Previous experiments have demonstrated flaws in the infusion set design, requiring human experiments to be suspended and modifications to the infusion set be made. We believe the current infusion set has addressed

these flaws by incorporating an anti-coring heel and a tri-beveled needle, and this sub-study is designed to isolate and study the infusion set function before further experiments using the iLet BP are conducted.

II. Hypothesis and Specific Aims

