- Medical, surgical and social history, allergies and review of systems relevant to inclusion and exclusion criteria
- Medications (prescription and non prescription)
- Type of insulin used in pump
- Average total daily dose in the last 30 days (from pump history)
- Height and weight
- Blood pressure
- Urine HCG (pre-menopausal females)
- Hemoglobin
- Hemoglobin a1c

During Study Visits:

- Insulin analog given
- Basal rates for the duration of the experiment, and carbohydrate ratio and correction factor used for the meal bolus
- Timing and content of the meal eaten, including carbohydrate count
- Timing and amount of insulin dose given for the meal
- Plasma glucose levels at least every 30 minutes, more frequently in the low range
- Plasma insulin levels every 20-30 minutes (assayed with Mercodia Iso-insulin ELISA)
- Total insulin given throughout the experiment
- Timing and amount of any carbohydrates taken for hypoglycemia
- Infusion site assessments including pain, skin reactions, appearance of site, and any evidence of leaks
- Timing of any infusion site replacements
- Subject reports of symptoms of any other complaints
- User satisfaction with both infusion sets

VI. b. Study Endpoints

VI. b. 1. Primary endpoint analyses

Aim 1: This will be generated from the bionic pancreas data during each arm:

- Average percent dose amounts calculated by the bionic pancreas control algorithm that are successfully delivered by the pump (aggregate of both insulin and glucagon doses).

Aim 2:

This will be generated from the bionic pancreas data during each arm:

- Average percent dose amounts calculated by the bionic pancreas control algorithm that are successfully delivered by the pump (glucagon doses).

Aim 4: Insulin Area Under the Curve in the 3.5 hours following the insulin bolus

VI. b. 2. Secondary endpoint analysis – Infusion Set Sub-Study

- During the initial 90 minute fasted period:
 - AUC
 - Mean insulin levels
 - Difference between insulin levels at baseline and at 90 minutes
- After the insulin dose:
 - T_{max}
 - T_{½max}
 - C_{max}
 - AUC in the first 30 minutes
 - AUC in the first 60 minutes
 - AUC in the first 90 minutes
 - Terminal half-life
- Difference between the fasted PG value and the PG value at 90 minutes
- Difference in PG prior to the meal and peak post-prandial glucose
- PG AUC in the 3.5 hours following the meal
- Number of infusion sites replaced for clinically suspected failure
- Local skin reactions
- Infusion site pain

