The main criteria for the success of the study will be that we observe a significant improvement in the primary outcome measure (and the related secondary reliability measures) in the iLet vs. the iPhone-based BPs, and no significant difference in the glycemic control measures. It is possible that improved reliability may actually improve glycemic control measures, but the sample size may not be sufficient to detect any such difference. A secondary criterion for success of the study will be that we observe no statistical difference in safety-related outcomes (occlusions, infusion site reactions or pain, nausea) between Xeris and Lilly glucagon.

The main criteria for the success of the infusion set sub-study will be that we observe no significant difference in the performance of the iLet infusion set when compared with the Contact Detach. Achieving a non-inferior result would allow us to move forward in future testing of the iLet infusion set with the iLet bionic pancreas in outpatient trials.

VII. Risks and Discomforts

Subjects may experience mild discomfort associated with the insertion of the infusion sets and sensor into the SC tissues. The risk of discomfort due to insertion of infusion sets and sensors is expected to be greater than in their lives outside the trial because more infusion sets will be inserted and a CGM sensor will be inserted, which may not be used in usual care.

There is a potential risk of hypoglycemia, since exogenous insulin will be administered. Due to frequent monitoring of glucose and direct supervision by an RN or MD at all times, the risk of a hypoglycemic episodes leading to significant harm to volunteers is expected to be substantially lower than their risk during their usual therapy.

There is a risk of hyperglycemia. This risk is expected to be less than the risk during the subjects' lives outside of the trial based on data from earlier trials.

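### Aim 1 hypothesises non-inferior dose delivery but is tested, sized and judged for superiority, with no margin, so a non-significant primary result could not be read against the hypothesis

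*Combined protocol and SAP*

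**What the plan says.** The objective for the Aim 1 comparison is worded in three ways.

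- **Section I.d (Rationale):** the study is meant "to establish equivalence between the two systems", with component reliability among the attributes listed, so that larger iLet studies can follow.
- **Section II (Hypothesis):** "We hypothesize that the iLet BP will be non-inferior to the iPhone-based BP in dose administration and blood glucose control".
- **Section VI.c (Power):** the calculation uses a two-sided 5% test and 80% power, and ends "so 10 subjects should provide sufficient power to detect a difference".
- **Section VI.d (Success):** the main criterion is that "we observe a significant improvement in the primary outcome measure", together with the related reliability measures, and that there is "no significant difference in the glycemic control measures".

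Section VI.b.1 defines the primary endpoint as the percentage of the calculated dose that the pump delivers, insulin and glucagon combined. The analysis text after section VI.b.5 offers a paired t-test or a Wilcoxon signed rank test, chosen by a Shapiro-Wilk test. No section states a non-inferiority or equivalence margin, or a rule based on a confidence interval.

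**The concern.** Non-inferiority, equivalence and superiority need different decision rules, and the plan has a rule only for superiority. If the paired test is significant in favour of the iLet, all is well. If it is not, the result is compatible with an iLet that is equally reliable, somewhat better or somewhat worse, and nothing tells the reader how to choose. Yet that distinction is what the hypothesis is about, and the rationale presents it as the ground for moving on.

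The glycemic half of the success rule has the opposite weakness. The hypothesis also covers glucose control, but success there means only the absence of a significant difference. In about 10 subjects that can happen because the data are imprecise, so it does not show non-inferiority. Read literally, a significant glycemic benefit of the iLet would also breach the rule.

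**Working it through.** **Inputs.** From section VI.c: iPhone system 96%; iLet 98%, 99.2% or 99.6% (2-, 5- and 10-fold reductions in unavailability); SD 2.5 in each arm; two-sided 5%; n = 10. The differences are 2.0, 3.2 and 3.6 points. Not in the documents, so assumed: within-subject correlation ρ of 0 and 0.5, and margins of 1, 1.5 and 2 points. Section VI.c uses pump availability as a stand-in for percent of dose delivered, and these figures inherit that.

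**Step 1: reproduce the plan's sample sizes.** Two independent samples, normal approximation, n per arm = 2 × [2.5 × (1.960 + 0.842) / difference]²:

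- 2.0 points: 24.5, rounded up to 25
- 3.2 points: 9.6, rounded up to 10
- 3.6 points: 7.6, rounded up to 8

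These match the stated 25, 10 and 8. They are sizes for detecting a difference, with no margin in the formula. The same method gives power at n = 10 of 43%, 82% and 90%.

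**Step 2: power of the planned paired t-test for superiority.** SD of the difference = 2.5 × √(2(1 − ρ)), which is 3.54 at ρ = 0 and 2.50 at ρ = 0.5. The standard error with n = 10 is 1.118 or 0.791. Power comes from the non-central t with 9 df, critical value 2.262 and non-centrality = difference / standard error.

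| True difference | Non-centrality (ρ = 0; 0.5) | Power, ρ = 0 | Power, ρ = 0.5 |
|---|---|---|---|
| 0 (equal) | 0; 0 | 2.5% | 2.5% |
| 2.0 (2-fold) | 1.79; 2.53 | 36% | 62% |
| 3.2 (5-fold) | 2.86; 4.05 | 72% | 95% |
| 3.6 (10-fold) | 3.22; 4.55 | 82% | 98% |

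**Step 3: power to show non-inferiority with the same data.** The rule is that the lower limit of the two-sided 95% interval lies above minus the margin. The calculation is as in step 2, with non-centrality = (difference + margin) / standard error.

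| True difference | Margin 1 (ρ = 0; 0.5) | Margin 1.5 (ρ = 0; 0.5) | Margin 2 (ρ = 0; 0.5) |
|---|---|---|---|
| 0 | 12%; 20% | 22%; 40% | 36%; 62% |
| 2.0 | 67%; 92% | 80%; 98% | 89%; 99% |
| 3.2 | 92%; >99% | 96%; >99% | 98%; >99% |

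A non-inferiority rule gains most when the iLet is moderately better. At truly equal reliability it succeeds more often than superiority does, but with these margins it still fails in 64% to 88% of trials at ρ = 0 and in 38% to 80% at ρ = 0.5.

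**The case against.** The best defence is that superiority was chosen on purpose. Section VI.c expects the iLet to be far more reliable because it removes the wireless link, and sizes the trial for at least a 5-fold reduction. The bar on the primary outcome is stricter than the hypothesis, so it cannot produce a false claim of non-inferiority. Rewording the hypothesis would cure the mismatch. All of this stands, and it is why restating the objective is one of the two remedies below. It does not settle which objective is meant.

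Three stronger readings are tempting, and the documents do not support them.

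- A reader might infer that the non-inferiority hypothesis is never tested. That goes too far: a significant improvement implies non-inferiority at any margin of zero or more. The gap opens only when superiority is not shown.
- A reader might take the 64% miss rate at a 2-fold reduction (100% − 36%, ρ = 0) as a defect of the sample size. Section VI.c itself says that scenario needs 25 subjects and makes no claim to power it with 10. It also argues that its SDs are probably too large.
- A reader might infer that missing the success criterion blocks larger studies. Section I.d gives equivalence as a rationale and ties no decision to this test. The one gate within the study, before the Aim 2 visits, is performance as expected (section II).

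On glycemia, section VI.d acknowledges that better reliability could improve control and that the sample may be too small to detect it. That is candid, but the rule still counts non-significance as success.

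**Conclusion.** The inconsistency is in the text and needs no assumption: non-inferiority and equivalence as objectives, superiority as test, sample size and success rule, and no margin anywhere. The consequence is limited to trials in which the primary test is not significant. By the planned paired t-test, that is 5% to 28% of trials at the expected 5-fold reduction, 38% to 64% at a 2-fold reduction and, counting only significance in the iLet's favour, 97.5% at equal reliability. These figures rest on the plan's SD of 2.5, on 10 completers and on an assumed correlation of 0 to 0.5; a higher correlation would raise power. The primary rule does not inflate false-positive claims. The glycemic rule is the more permissive half, since imprecise data help to satisfy it. Should-fix.

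**What to change.** Before any data are seen, do one of the following for dose delivery.

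1. **Restate the objective.** Change sections I.d and II so that the aim for dose delivery is superiority, in line with sections VI.c and VI.d.
2. **Add a non-inferiority step.** State a margin in percentage points of dose delivered and justify it clinically and technically; the documents supply no basis for one, and the 1 to 2 points used above are only illustrative. Declare non-inferiority if the lower limit of the two-sided 95% interval for the paired difference lies above minus the margin, then test superiority at the same alpha in fixed sequence. If the Shapiro-Wilk check leads to the Wilcoxon test, use the matching Hodges-Lehmann interval.

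Under either choice, report the interval. For the glycemic measures, replace the requirement of no significant difference in section VI.d with an interval rule against a stated margin, worded so that a benefit does not count as failure.

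The cost is protocol wording and the work of justifying margins. There is no alpha penalty and no subjects need be added. The downside of option 2 should be stated in the plan: with 10 subjects and truly equal reliability, power at margins of 1 to 2 points is about 12% to 36% (correlation 0) or 20% to 62% (correlation 0.5), so a failed first step would be inconclusive and not evidence that the iLet is worse.
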